6.2.3 Outcome assessment

Our primary outcome is **improved dementia care**. This outcome is collected prospectively from EMR and related medical records by data analysts and do not require patient interviews. This primary outcome is defined as meeting any one of the following endpoints within 90 days of the clinic visit at which the patient was randomized.

1. New diagnosis of dementia (relevant ICD-10 codes) or MCI (331.83) documented in the EMR. The recent DSM-V criteria³⁷ include categories of ‘major neurocognitive disorder’ and ‘mild neurocognitive disorder,’ which overlap with dementia and MCI. These categories will also be included but a recent internal audit indicated that they are as yet not in widespread use in our primary care clinics (cf. specialty clinics).
2. Tests ordered for reversible causes of cognitive impairment as recommended by the published guidelines of professional societies (e.g. thyroid function tests, B-12 level, CT or MRI scans).^{15, 38-41}
3. New prescriptions for dementia medications in EMR.
4. Referral for cognitive/dementia evaluation by specialists (Neurology, Geriatrics or Psychiatry) in EMR.

7 SAFETY ASSESSMENTS

Participant safety will be monitored once an individual is enrolled in the study. We do not expect any serious adverse events during the non-invasive assessments that will take place in both study arms. Answering health questionnaires and cognitive assessments involve minimal psychological, social, or other risks.

7.1 Specification of Safety Parameters

Trained RAs, who will monitor the subject for any adverse events, will perform all assessments. The RA will stop the testing procedures if subjects feel stressed or get embarrassed by their performance, and relay the information immediately to [name] or one of the supervising clinicians (Drs. [name], [name], [name], or [name]). In addition, [name] and [name] will be available at the clinic site during the conduct of the trial, and [name] will be available by cellular telephone at all times to address any safety concerns or clinical issues.

All abnormal findings from the clinical, motor, and neuropsychological assessments will be documented and the participant and their primary care physician will be informed of all clinical results that are relevant to patient care following the 90 day window for primary outcome ascertainment.

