- b) **Neuropsychological Battery (exploratory outcome):** The battery will take 60 minutes to complete and will include the measures below (Table 1). The tests are selected from those used for diagnostic testing in our dementia clinic, and with established norms for different ethnic groups and educational levels.¹⁴ The battery will be supervised by [name] (Cognitive Core); blinded to 5-Cog results. The battery is administered in English or Spanish to probe general mental status (MoCA) as well as specific cognitive domains, particularly memory (Hopkins Verbal Learning Test-R⁴⁵), processing speed (Symbol Digit Modalities Test⁴⁶), language (letter fluency,^{47, 48} category fluency,⁴⁸ Boston Naming Test⁴⁸), and visuo-spatial abilities (clock drawing¹²).⁴⁹ For ethical reasons, if results from the neuropsychological testing are in the dementia range, [name] will inform the treating physician after the 90-day window to determine improved dementia care outcomes.

Table 1. Neuropsychological Assessments

Domain	Tasks
Mental Status	MoCA
Premorbid Estimate/ Reading ability	Wechsler Test of Adult Reading (WTAR)/ Word Accentuation Test (TAP)
Memory	Hopkins Verbal Learning Test- R(HVLT-R)
Naming	Boston Naming- Short Form
Fluency	Controlled Oral Word Association Test (FAS); Animals
Timed Transcription	Symbol Digit Modalities Test
Clock	Clock Drawing Test
Mood	Geriatric Depression Scale-30 item

c) **Advance care planning (exploratory outcome):** We will explore whether 5-Cog screening leads to higher rates of advance care planning such as referrals to social work or Alzheimer's Association or having health care proxies or living wills recorded in the EMR.

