7.4 Reporting Procedures

AE Reporting: All AEs will be collected on an Adverse Event Form in electronic format and recorded in the RedCap database. All AEs experienced by the participant will be reported in Safety Reports sent twice a year to the NINDS Program Official.

SAEs Reporting: When SAEs occur that are unanticipated (i.e., events other than those described in the protocol, consent form and DSMP), and that are related to the intervention, they will be reported to NINDS Program Officer within 48 hours of study's knowledge of the SAE. The expedited report will be followed by a detailed, written SAE report as soon as possible. Follow up information may be required.

Relatedness: The potential event relationship to the study intervention and/or participation is assessed by the site investigator. The comprehensive scale to categorize an event is listed below:

- Definitely Related: The AE is clearly related to the investigational procedure – i.e. an event that follows a reasonable temporal sequence from administration of the study intervention, follows a known or expected response pattern to the suspected intervention, that is confirmed by improvement on stopping and reappearance of the event on repeated exposure and that could not be reasonably explained by the known characteristics of the subject's clinical state.
- Possibly Related: An AE that follows a reasonable temporal sequence from administration of the study intervention follows a known or expected response pattern to the suspected intervention, but that could readily have been produced by a number of other factors.
- Not Related: The AE is clearly not related to the investigational procedure - i.e. another cause of the event is most plausible; and/or a clinically plausible temporal sequence is inconsistent with the onset of the event and the study intervention and/or a causal relationship is considered biologically implausible.

Expectedness: AEs must be assessed as to whether they were expected to occur or unexpected, meaning not anticipated based on current knowledge found in the protocol and the consent form. Categories are:

- **Unexpected:** The nature or severity of the event is not consistent with information about the condition under study or intervention in the protocol or consent form.
- **Expected:** The event is known to be associated with the intervention or population under study.

Classification of AE Severity:

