9.3 Interim analyses and Stopping Rules

Due to the non-invasive nature of the protocol, it is not expected that early termination will be required due to adverse events. However, constant monitoring of the participants by [name], other investigators, and research staff will be maintained to ensure that AEs are not occurring. Early study termination will occur in the event of any unanticipated serious adverse event determined to be possibly, probably or definitely related to study procedures.

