10.3.4 Monitoring

A study protocol, Manual of Operations and DSMP for all study activities will be developed during study setup and approved by the IRB and internal safety monitoring committee prior to initiating recruitment. Data will be maintained in a Database Manager System (RedCap).

The database system will have automated checks for ranges of values and logical validity of data entered and will be programmed to import subject data directly from the computerized test data files. Imported data files will be checked for data integrity and flagged in the event of inconsistent or missing data. Hand entered data will be verified using double entry routines to guard against key punch errors. This system will provide

immediate access to individual subject data and can generate a summary report of the entire database. The database will contain provisions for password protection and distribution of analytic data files containing only necessary information on an as-needed basis; there will be an interface to export all or selected data from RedCap and transfer these to any of the statistical packages (SAS, S-PLUS, Stata, SPSS) used by the project investigators.

Full backups of the entire database will be performed daily. For added security, copies of the databases are kept in two separate physical locations in locked, fire-resistant containers. Database files will be maintained by the Database Management Core and subjected to quality control procedures. Summary reports will be generated and reviewed by the project manager and PI as requested.

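### As worded, the 90-day hold in section 7.1 covers a severe depression score, and no text in the documents directs that such a score be passed on sooner

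*Combined protocol and SAP*

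**What the plan says.** Section 7.1 says that abnormal clinical, motor and neuropsychological findings will be documented. It then says that the participant and the primary care physician will be "informed of all clinical results that are relevant to patient care following the 90 day window" for ascertaining the primary outcome.

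Table 1 in section 3, which lists the neuropsychological assessments, includes a Mood entry: "Geriatric Depression Scale-30 item".

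Section 3, item b, has a narrower disclosure rule. The treating physician is told after the 90-day window "if results from the neuropsychological testing are in the dementia range".

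The plan also contains safeguards:

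- Section 3, item b: "The battery will be supervised by" a member of the Cognitive Core.
- Section 7.1: clinicians are available at the clinic site, and one "will be available by cellular telephone at all times to address any safety concerns or clinical issues".
- Sections 7.1 and 7.6: if a participant becomes stressed or embarrassed during testing, the tester stops and tells a supervising clinician at once.
- Section 9.3: constant monitoring of participants by a named lead, "other investigators, and research staff will be maintained to ensure that AEs are not occurring".

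**The concern.** A timing rule meant to protect the 90-day outcome from cognitive disclosures is written broadly enough to take in a mood score. The patient's clinician cannot act on that score at the enrollment visit. Under section 3 the battery follows the clinician's consultation, and under section 6.2.2 it may be done by telephone or video from July 27, 2020. Staff who follow the 7.1 sentence as it stands could therefore leave a severe-range depression score unreported to patient and physician until the window has closed.

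What is at stake is participant safety, not inference about the 5-Cog.

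**Working it through.** No figure in the plan needs reproducing. The check sets the sections side by side.

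**1. Scope of the two disclosure rules**

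| | Section 3, item b | Section 7.1 |
|---|---|---|
| Findings | Dementia-range neuropsychological results | Care-relevant results, following a sentence that spans abnormal clinical, motor and neuropsychological findings |
| Who is told | Treating physician | Participant and primary care physician |
| When | After the 90-day window | After the 90-day window |

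Section 7.1 is broader in both findings and recipients. The timing phrase in 7.1 could grammatically attach to relevance rather than to informing. The natural reading, supported by item b, is that it says when people are told.

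**2. Does 7.1 reach the depression scale?** Table 1 lists the scale among the neuropsychological assessments, and 7.1 makes no exception for it. As worded, yes.

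**3. Does the outcome justify the wait?** Section 6.2.3 gives four components: a new dementia or MCI diagnosis, tests for reversible causes, dementia medication, and specialist referral for cognitive evaluation. A cognitive result disclosed early could trigger any of them directly. Mood is not among them, so the reason for holding cognitive results applies only weakly to a mood score.

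**4. Does any text direct earlier relay?** The one immediate-relay instruction (7.1, repeated in 7.6) is triggered by distress during testing, not by a score. Battery supervision, clinician availability and adverse-event monitoring permit escalation, but none sets a score threshold or requires a score to be passed on. The amendment log records the remote option with no accompanying mood-score rule.

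**5. Length of the hold.** Let *d* be the number of days from the randomization visit to the battery. The part of the delay due to the window is 90 − *d* days:

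- Same-visit battery: *d* = 0, so 90 − 0 = 90 days.
- Remote battery: 90 − *d* days; the protocol gives no timing for *d*.

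Section 7.1 sets no deadline for telling people once the window has closed.

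**6. Number affected.** This would be 1,200 × *c* × *p*, with *c* the battery completion rate and *p* the proportion of completers scoring in the severe range. Section 6.2.2 allows for 50% non-completion, which would leave 1,200 × 0.5 = 600, but that is a planning tolerance, not an expected rate. The documents give no severe-range cut-off and no value for *p*, so the product cannot be evaluated.

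**The case against.** The strongest reply is that 7.1 should be read by its purpose. The hold is tied to the outcome window, mood is not in the outcome, and item b is the specific rule. The sentence cannot be meant literally either, because it names motor findings while section 5.1 sends the 5-Cog results, gait included, to the physician at the same visit. On that reading only cognitive results are held. This is reasonable and softens the point, but 7.1 does not say it, and testers should not have to infer an exception to a safety instruction.

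A reader might infer that early action on a mood score is forbidden. The text does not go that far. It sets a time for informing people and contains no ban on earlier contact, and the preceding paragraph makes clinicians available for clinical issues. They may act sooner; they are not told to.

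A reader might also infer that the trial has no rule at all. The documents cannot show that. Section 10.3.4 says "A study protocol, Manual of Operations and DSMP for all study activities will be developed during study setup", with approval before recruitment. Neither the Manual of Operations nor the DSMP was available, and the consent pages were removed before review. The finding is limited to the text supplied.

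Finally, a reader might argue that a severe score would go down the adverse-event route and so bypass the physician, since section 7.4 says "All AEs experienced by the participant will be reported in Safety Reports sent twice a year to the NINDS Program Official". That is hypothetical. Nothing says a score from this battery is recorded as an adverse event, and 7.4 governs reporting to the funder without restricting clinical communication.

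**Conclusion.** The point holds as a drafting gap with a safety consequence. The 7.1 wording defers disclosure of a severe depression score by up to 90 days on account of the window, item b does not require this, and no available text directs earlier relay.

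The conclusion rests on three assumptions: that the timing phrase governs when people are informed, that Table 1 defines which tests count as neuropsychological, and that staff follow the sentence as written. A suitable rule in the Manual of Operations or the DSMP would reduce the problem to a missing cross-reference.

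It would be tempting to conclude that the hold biases the treatment comparison. The documents do not support that: the hold is the same in both arms and concerns a measure outside the primary outcome. Nor do they support any count of participants harmed. The change is worth making because it is inexpensive; confidence is medium, given the documents not seen.

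**What to change.** Amend section 7.1 to say that:

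1. The 90-day hold applies only to cognitive results from the post-visit battery, consistent with section 3, item b.
2. A depression score at or above a severe-range threshold, set by the supervising clinicians, is relayed promptly to a supervising clinician and to the primary care physician. This applies in both arms and to in-person and remote batteries, and no cognitive scores are sent with it. The EMR message route in section 5.1 can carry it.
3. The date of each such disclosure is logged.

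If the Manual of Operations or the DSMP already contains a rule of this kind, cite it in 7.1 instead.

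The cost is protocol wording, an IRB amendment, a log, and a small workload for prompt scoring and relay. The downside is that a disclosure may occasionally prompt a work-up, including blood tests or imaging, or a cognitive referral that counts under component 2 or 4, in either arm. A psychiatry referral for mood alone already falls outside component 4, so that definition needs no change.

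I would not add a sensitivity analysis that discounts orders made after a disclosure. It would select on a post-randomization event among those who took an optional battery, and a version limited to blood tests would miss imaging and referrals. The log is enough to describe how often disclosure occurred in each arm.

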7.2 Methods and Timing for Assessing, Recording, and Analyzing Safety Parameters

7.3 Adverse Events and Serious Adverse Events

Adverse Events (AEs): Any untoward or unfavorable medical occurrence in a human subject, including any abnormal sign (for example, abnormal physical exam or laboratory finding), symptom, or disease, temporally associated with the subject's participation in the research, whether or not considered related to the subject's participation in the research. AEs encompass both physical and/or psychological harms.

Serious Adverse Events (SAEs): An adverse event that meets any of the following criteria:

- Results in death
- Is life threatening, or places the participant at immediate risk of death from the event as it occurred
- Requires prolonged hospitalization
- Causes persistent or significant disability or incapacity
- Is another condition which investigators judge to represent significant hazards

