4.1 Inclusion Criteria

1) Age 65 and older. **2)** Presence of cognitive concerns expressed by patient or caregiver or identified by health care providers. **3)** Registered as patient at Montefiore Medical Center and have a primary care doctor appointment that day. **4)** Able to see and hear well enough to complete intervention or control assessments. **5)** English or Spanish speaking.

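### Section 7.3 counts hospitalization as serious only when prolonged, with no length given, so a related, unanticipated admission of ordinary length can miss the 48-hour report and the section 9.3 rule

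*Combined protocol and SAP*

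**What the plan says.** All references are to the combined protocol and SAP.

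- **Section 7.3** lists five SAE criteria, any one of which is enough: death, threat to life, "Requires prolonged hospitalization", lasting or significant disability, and a discretionary criterion, "Is another condition which investigators judge to represent significant hazards". Only the third names hospitalization.
- **Section 4.1** requires that participants "have a primary care doctor appointment that day", so they enter as outpatients.
- **Section 7.4, expedited route.** If an SAE is both unanticipated and related, "they will be reported to NINDS Program Officer within 48 hours". Unanticipated means "events other than those described in the protocol, consent form and DSMP".
- **Section 7.4, routine route.** "All AEs experienced by the participant will be reported in Safety Reports sent twice a year to the NINDS Program Official".
- **Section 7.4, severity.** The top severity grade mentions that admission may occur. A note then says that severity and seriousness are different things.
- **Section 7.6** draws the internal safety committee from the project's own investigators.
- **Section 9.3** makes early termination mandatory for any unanticipated SAE that is at least possibly related to study procedures.

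**The concern.** SAE status is the gate to two consequences: the 48-hour notice in 7.4 and the termination rule in 9.3. If the definition leaves out an ordinary new admission, both are bypassed, however clearly the event is related and unanticipated. Two investigators could classify the same two-night stay differently and both be following the protocol.

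The 48-hour report matters more here than it might elsewhere. Because the safety committee consists of project investigators, that report is the only expedited event notice to anyone outside the project team that the visible text states. IRB rules or the DSMP may add others. Local clinicians may know of the event at once. What can be late is the outside report, and what can be skipped is consideration under 9.3.

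**Working it through.** There is no stated figure to reproduce. The check is a trace through the text, then the size of the delay.

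**1. Does either reading of the hospitalization line cover a new, ordinary-length admission?**

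- Read as a long stay: the line has no threshold, and a short stay is outside it on any natural meaning.
- Read as the lengthening of a stay already under way: someone who came in as an outpatient normally has no such stay, so a new admission is outside it.

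Neither reading covers it.

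**2. Does any other text close the gap?** The remaining mentions of hospitalization concern utilization (sections 1.2, 3, 9.4.2 and 9.5), capture in the electronic medical record (10.3.2) and the severity grade (7.4). None defines the term or makes admission a seriousness criterion. The severity note points the other way, since it allows for a hospitalized event that is graded severe but is not serious.

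**3. Trace one event.** Take an admission that is related, unanticipated, of ordinary length, neither fatal nor life-threatening, and not disabling.

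- If investigators apply the discretionary criterion, it is an SAE. The 48-hour report follows, and 9.3 applies.
- If they do not, it meets none of the five criteria. It is an adverse event only, goes into the next twice-yearly report, and 9.3 is not engaged.

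The miss is possible but not built in.

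**4. Size of the delay.** Inputs: 48 hours and twice a year, both from 7.4. Assumptions: reports evenly spaced, event times uniform between reports.

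- Expedited route: 48 / 24 = 2 days.
- Routine route, longest wait: 365.25 / 2 = 182.6 days.
- Routine route, mean wait: 182.6 / 2 = 91.3 days.
- Extra delay: 182.6 − 2 = 180.6 days at most, and 91.3 − 2 = 89.3 days on average.

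With unevenly spaced reports the longest wait could exceed this.

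**5. How many events?** The documents give no rate, so no count can be derived from them. For scale only, assume that between 1 in 10,000 and 1 in 2,000 of the 1,200 participants have such an admission:

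- 1,200 × 0.0001 = 0.12
- 1,200 × 0.0005 = 0.60

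Under that assumption, fewer than one event is expected in the whole trial.

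**The case against.** The strongest reply is that nothing of consequence is shown.

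- The procedures are short paper, gait and grip tests plus an optional longer battery, and section 7 expects no serious events.
- Several conditions must coincide before a report is late. The last is that investigators decline to use a criterion they already have, when an unexpected admission caused by a minimal-risk test is an obvious candidate for it.
- Every adverse event is still recorded and reaches the funder twice a year, and 9.3 commits the investigators to continuous monitoring.
- Section 10.3.4 calls for a DSMP and a Manual of Operations, either of which may define the term.
- A narrower threshold might be deliberate in a low-risk trial of older patients, for whom admission is also a tracked outcome.
- Widening 7.3 alone would make 9.3 easier to trigger. Section 7.4 lets an event count as possibly related when it fits in time "but that could readily have been produced by a number of other factors". Asking the committee how it reads 9.3 would not change a mandatory rule.

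Most of this stands. It limits the weight of the point and decides the form of the remedy: 9.3 must be edited in the same step. It does not remove the gap. The discretionary criterion leaves the decision to the project's own investigators. The 48-hour rule exists for events nobody foresaw, so a low expected count does not justify an undefined gate. The protocol gives no sign that the narrower threshold was chosen on purpose. If the DSMP is clearer, the protocol should agree with it.

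**Conclusion.** The point holds as a wording gap of low priority. As written, 7.3 can send a related, unanticipated, ordinary-length admission to the twice-yearly report instead of the 48-hour one, and outside 9.3. The cost is a delay of up to about 183 days in place of 2, given evenly spaced reports. The number of events is unknown from the documents and probably very small. The primary analysis is unaffected.

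A reader might infer more: that reportable hospitalizations will go unreported, or that some known share of participants' admissions escapes safety review. The documents do not support that. The discretionary criterion may capture such events, and all adverse events are reported in the end. Admissions known in this population may be classed as expected. The consent form and DSMP, which help decide what is unanticipated, cannot be seen, so no particular event can be said to qualify.

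**What to change.** Make three changes in one amendment.

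1. In 7.3, replace the hospitalization line with: *Requires inpatient hospitalization or prolongs an existing hospitalization.*
2. Use the same wording in the DSMP and the Manual of Operations.
3. Reword 9.3 so that an unanticipated SAE judged only possibly related leads to a pause and safety committee review, not automatic termination. The new text should use the relatedness levels of 7.4, which has no *probably* level although 9.3 names one.

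The first change should not be made without the third, or one admission with a loose link to the study could end the trial.

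**Cost.** A few sentences and an IRB amendment. Admissions within the health system are already captured (10.3.2), so they need no new data collection. More events will carry the SAE label. As an upper bound, assume that 5% to 25% of participants are admitted within 12 months and that every admission is recorded as an adverse event: 1,200 × 0.05 = 60 to 1,200 × 0.25 = 300 participants. The extra work for each is modest. Relatedness is already judged under 7.4, and "AEs must be assessed as to whether they were expected to occur or unexpected", so the added step is the seriousness label. Only related and unanticipated cases would need the 48-hour report.
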